8.5. Safety Analysis

Adverse events will be summarized for all treated subjects (safety population) and will be presented by Medical Dictionary for Regulatory Activities preferred term and primary system organ class, and by group and treatment as the number of AEs and the number (percentage) of subjects with AEs. The percentage of subjects with AEs will be compared between treatments by a chi-square test or Fisher's exact test.

Vital signs, ECG, and laboratory parameters will be summarized by descriptive statistics (actual values and changes from baseline) at each assessment timepoint by group and treatment and by shift tables (according to normal ranges).

No formal statistical analysis of safety data is planned.

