## 2. STUDY OBJECTIVES

**Table 1: Objectives and Endpoints**

Objectives	Endpoints
Primary:	

to evaluate the safety and tolerability of single and multiple ascending oral doses of AQ280, and to determine a safe therapeutic range of AQ280 in healthy subjects

	

number of TEAEs per subject

clinically significant abnormalities in vital signs (systolic and diastolic blood pressure, pulse rate, and oral body temperature)

abnormal ECG (QTcF interval of >450 msec for males and >470 msec for females, or change from baseline of >30 msec) measured from Day 1 (postdose) up until 48 hours postdose in Part A and up to the follow-up visit in Part B

clinically significant changes in laboratory evaluations

Objectives	Endpoints

Secondary:
 
 
• to determine the PK of AQ280 after single and multiple oral doses
 
• to determine the PK of the AQ280 main metabolite, AQ282, after single and multiple oral doses
 
• to determine the effect of food on the PK of AQ280 after single oral dose
 
	
Part A (SAD):
 
 
• primary PK parameters derived from plasma concentration-time profile of AQ280: <math>AUC_{0-\infty}</math>, <math>C_{max}</math> (<math>AUC_{0-t_{last}}</math> may be included as a primary PK parameter if <math>AUC_{0-\infty}</math> cannot be calculated)
 
• primary PK parameters derived from plasma concentration-time profile of the AQ280 main metabolite, AQ282: <math>AUC_{0-\infty}</math>, <math>C_{max}</math> (<math>AUC_{0-t_{last}}</math> may be included as a primary PK parameter if <math>AUC_{0-\infty}</math> cannot be calculated)
 
• comparison of the primary PK parameters of AQ280 after single dose administration in the fasted state and in the fed state
 
 
Part B (MAD):
 
 
• primary PK parameters derived from plasma concentration-time profile of AQ280 on Day 1 and Day 7: AR, <math>AUC_t</math>, <math>C_{max}</math>
 
• primary PK parameters derived from plasma concentration-time profile of the AQ280 main metabolite, AQ282, on Day 1 and Day 7: <math>AUC_t</math>, <math>C_{max}</math>
 

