### 3.1.2. Part B (Multiple Ascending Dose)

Part B will comprise a multiple-dose, sequential group, escalating-dose design conducted in healthy adult male and female subjects. Part B may start prior to completion of all planned dose groups in Part A, at a dose equal to or less than that evaluated as safe and well tolerated in Part A.

A total of approximately 24 subjects are planned to be studied in 3 groups (Groups B1 to B3). In each group, 6 subjects will receive AQ280 and 2 subjects will receive placebo. Each group should contain both male and female subjects, preferably at least 2 subjects of each gender. Additional groups may be added based on the need for more evaluations or groups removed based on data obtained.

There will be a minimum of 9 days between dose escalations for each group.

Potential subjects will be screened to assess their eligibility to enter the study from 2 days up to 5 weeks before the first dose of AQ280 or placebo. Each subject will participate in 1 group only and reside at the study site from Days -1 to 9.

For all subjects, dosing is planned to be once daily (QD) on Days 1 to 7, inclusive, at approximately the same time each morning. The dosing regimen in Part B may be changed following review of preliminary data from groups in Part A or previous groups in Part B. The daily dose administered, when given repeatedly, will be predicted to not exceed an exposure shown to be safe and well tolerated in Part A. Dietary state will be determined based on data obtained in Part A.

A safety follow-up visit will be conducted 1 week ( $\pm 3$  days) after the final dose.

Based on the ongoing review of the safety, tolerability, and PK results, additional outpatient visits may be required.

[figure not shown]
Safety assessments will include AE reporting, vital signs, ECGs, clinical laboratory tests, and physical examination.

Blood samples to determine the PK of AQ280 and its main metabolite, AQ282, will be collected from predose up to 24 hours postdose on Day 1; predose on Days 3 through 6; and from predose up to 48 hours postdose on Day 7.

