**Table 2: Presentation of Study Treatments in TFLs (Part A)**

Part	Group	Study Treatment	Order in TFLs
A	A1 to A5	Placebo	1
	A1	3 mg AQ280 (Fasted)	2
	A2	XX mg AQ280 (Fasted)	3
	A3	XX mg AQ280 (Fasted)	4
		XX mg AQ280 (Fed)	5
	A4	XX mg AQ280 (Fasted)	6
	A5	XX mg AQ280 (Fasted)	7

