**Table 3: Presentation of Study Treatment Sequences in TFLs (Part A; Food-effect Group Only)**

Group	Study Treatment Sequence	Order in TFLs
A3	Placebo (Fasted) / Placebo (Fed)	1
	XX mg AQ280 (Fasted) / XX mg AQ280 (Fed)	2

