## 7.7. Safety and Tolerability Assessments

### 7.7.1. Adverse Events

All AEs will be coded using the Medical Dictionary for Regulatory Activities (MedDRA) Version 25.0 (or higher if a new version is issued during the study; see the DMP for more details).

A treatment-emergent adverse event (TEAE) will be defined as an AE that starts during or after the first dose, or starts prior to the first dose and increases in severity after the first dose.

A treatment-related TEAE will be defined as a TEAE with a relationship of possibly related or related to the study treatment, as determined by the investigator.

All AEs will be listed. In addition to the data recorded in the database, the listings will include derived onset time and duration. Onset time will be calculated from the time of the last associated dose for TEAEs only. Where the last associated dose is referring to the last dose received prior to the start of a TEAE.

The frequency of subjects with TEAEs and the number of TEAEs will be summarized for the following categories:

- TEAEs (overall, serious, leading to discontinuation, and leading to death) by treatment
- TEAEs by severity and treatment
- Treatment-related TEAEs (overall, serious, leading to discontinuation, and leading to death) by treatment
- Treatment-related TEAEs by severity and treatment

The frequency of subjects will be summarized separately for TEAEs and treatment-related TEAEs by the following:

- System organ class, preferred term, and treatment
- Preferred term and treatment

For the AE data the following rules will apply:

- For the derivation of treatment-emergent status (applicable to all AEs): If the start date/time of an AE is incomplete or missing, an AE will be assumed to not be a TEAE, unless the incomplete start date/time or the end date/time indicates an AE started after the first dose.
- For the derivation of treatment-related status (applicable to TEAEs only): If the study treatment relationship for a TEAE is missing, a TEAE will be assumed to not be a treatment-related TEAE.

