- For the derivation of onset time (applicable to TEAEs only): If the start date/time of a TEAE is missing, onset time will not be calculated. If the start date/time of a TEAE is incomplete, where possible, the minimum possible onset time will be calculated and presented in ‘ $\geq$ DD:HH:MM’ format (eg, if the date/time of the last associated dose is 01MAY2019/08:00 and recorded start date/time of a TEAE is 03MAY2019, then the minimum possible onset time will be calculated by assuming a TEAE started at the first hour and minute of 03MAY2019 [03MAY2019/00:00], thus will be presented as onset time  $\geq$ 01:16:00 in the listing). If the start date of a TEAE is the same as the date of the last associated dose but the start time of a TEAE is missing, an onset time will be presented as ‘ $\geq$ 00:00:01’. Any clock changes will be accounted for in the derivation.
- For the derivation of duration (applicable to all AEs): If the end date/time of an AE is missing, duration will not be calculated. If the start or end date/time of an AE is incomplete, where possible, the maximum possible duration will be calculated and presented in ‘ $\leq$ DD:HH:MM’ format (eg, if the start of an AE date/time is 01MAY2019/08:00 and its recorded end date/time is 03MAY2019, then the maximum possible duration will be calculated by assuming an AE ended at the last hour and minute of 03MAY2019 [03MAY2019/23:59], thus will be presented as duration  $\leq$ 02:15:59 in the listing). Any clock changes will be accounted for in the derivation.
- For the calculation of TEAE summary statistics: If the severity of a TEAE is missing, that TEAE will be counted under the ‘missing’ category.
- For the calculation of TEAE summary statistics: If a subject experienced multiple TEAEs with the same preferred term for the same treatment, this will be counted as 1 TEAE for that treatment under the maximum severity recorded.

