## **9. SIGNIFICANT CHANGES FROM THE PROTOCOL-SPECIFIED ANALYSES**

The statistical analysis for the food effect group (A3) was changed to use a mixed model which differs from the stated analysis of variance model in the protocol.

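### The SAP's rule for repeated TEAEs turns the number of TEAEs into a count of distinct subject, preferred term and treatment combinations, so recurrent events are understated, mainly in Part B

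*SAP*

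**What the plan says.** The primary endpoints in Protocol Table 2 and SAP Table 1 begin with "number of TEAEs per subject". Protocol Section 8.5 presents adverse events "by group and treatment as the number of AEs and the number (percentage) of subjects with AEs", with no merging of repeats.

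SAP Section 7.7.1 keeps the same two quantities apart: "The frequency of subjects with TEAEs and the number of TEAEs will be summarized for the following categories". Four categories follow: TEAEs overall, TEAEs by severity, treatment-related TEAEs overall, and treatment-related TEAEs by severity. The system organ class and preferred term tables give subject frequencies only.

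The section closes with derivation rules. The last one, introduced as applying to TEAE summary statistics in general, concerns a subject with several "TEAEs with the same preferred term for the same treatment, this will be counted as 1 TEAE for that treatment under the maximum severity recorded".

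SAP Section 9 lists one departure from the protocol's analyses: "The statistical analysis for the food effect group (A3) was changed to use a mixed model".

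**The concern.** A rule that counts a subject once per preferred term at worst severity is standard for subject counts. This rule is worded as a count of TEAEs, and the only planned outputs that count TEAEs are the four-category summaries. A programmer who follows the text would therefore apply it to the event count.

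A subject with the same symptom after every dose would then add the same amount to the number of TEAEs as a subject who had it once. Recurrence on repeated dosing is something a multiple-dose tolerability part should show, and the rule removes it from the headline count for the first-listed primary endpoint. It also shifts severity: if the repeats differ in grade, the milder ones disappear and only the worst remains.

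The SAP says that it supersedes the protocol's statistical considerations and that substantial differences will be identified. If the collapsed count is intended, it has not been identified.

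**Working it through.** **1. Scope of the rule.**
- The lead-in refers to TEAE summary statistics without restriction. Other rules in the same list do state limits, for example to TEAEs only.
- The unit is one TEAE, not one subject.
- Two of the four event-count categories are not by severity, and the by-severity categories also count events. Reading the rule as severity-only therefore does not leave an uncollapsed count.
- No other part of the SAP text defines the event count.

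**2. Where repeats can occur under one treatment label.**
- Part B: "dosing is planned to be once daily (QD) on Days 1 to 7, inclusive, at approximately the same time each morning", under one label per group (SAP Table 4). Each group has 6 active subjects, so 6 × 7 = 42 subject-doses.
- Part A, active: one dose per treatment. Fasted and fed dosing in Group A3 are separate treatments in SAP Table 2, so the two periods are not merged. Only recurrence after a single dose is affected.
- Part A, placebo: SAP Table 2 pools placebo from A1 to A5 as one treatment, while SAP Table 3 names a fasted/fed placebo sequence. The two A3 placebo periods may or may not be merged.

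**3. Size in Part B.** The documents state no event or recurrence rate, so there is no figure to reproduce. Assume that one preferred term occurs with probability *p* after each dose, at most once per dose, independently between doses, and is recorded as a new AE each time.

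- All events: 42*p*
- Events under the rule: 6[1 − (1 − *p*)^7]

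| *p* (assumed) | All events | Under the rule | Kept |
|---|---|---|---|
| 0.05 | 2.10 | 1.81 | 86% |
| 0.1 | 4.20 | 3.13 | 75% |
| 0.2 | 8.40 | 4.74 | 56% |
| 0.5 | 21.0 | 5.95 | 28% |

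Whatever the recurrence, the group's count for one term cannot exceed 6. If the term followed all 42 subject-doses, 6 would be counted, an understatement of 1 − 6/42 = 86%.

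**4. Contrast with placebo.** Pooled Part B placebo is 3 groups × 2 = 6 subjects, the same size as one active group, so the same table applies. With *p* = 0.2 on active and 0.05 on placebo, the event ratio is 8.40/2.10 = 4.0, but 4.74/1.81 = 2.6 under the rule. With 0.5 against 0.1 it is 21.0/4.20 = 5.0, but 5.95/3.13 = 1.9.

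**5. Size for Part A placebo if the A3 periods are merged.** There are 5 × 2 = 10 placebo subjects. Eight have one dose and the two in A3 have two, so there are 12 doses.

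- All events: 12*p*
- Events under the rule: 8*p* + 2[1 − (1 − *p*)²]

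For *p* = 0.05 this gives 0.600 against 0.595 (99% kept); for 0.2, 2.40 against 2.32 (97%); for 0.5, 6.00 against 5.50 (92%).

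**The case against.** **Intent.** The rule just before it has the same lead-in and deals only with missing severity, and the disputed rule ends with maximum severity. Together they may be meant only to stop one episode, recorded at several grades, from being counted several times. This is plausible, but the text does not say so, and the by-severity tables count events too.

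**Operational definition.** Neither the endpoint nor Protocol Section 8.5 says how repeats are counted, and the SAP supersedes the protocol, so the rule could be the chosen definition. In that case it changes how a primary endpoint is counted and should be declared.

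**Size.** The percentages need an assumed rate, independence between doses and a new AE record for each recurrence. The documents do not settle the last point: if a daily symptom is entered as one continuing AE, the loss is zero. The figures are also for one term. Across all TEAEs the proportion kept is the event-weighted average over terms, and it is close to 100% when events are spread over many terms that seldom recur. This objection stands in full.

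**Consequence.** Every AE is listed with onset and duration, so recurrences can be recovered. Subject percentages do not change. The stopping criteria in Protocol Section 3.7 count subjects or use exposure limits. SAP Section 7.7.6 plans no inferential safety analysis. The table shells, which were not available, might define the count differently. All of this limits the damage, but listings do not correct a headline count.

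**Conclusion.** The point holds. As written, the number of TEAEs is the number of distinct subject, preferred term and treatment combinations. That is a different quantity from the event count named in the primary endpoint and in Protocol Section 8.5, and Section 9 does not declare it. The wording of the rule establishes this; whether it was intended cannot be told from the documents.

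The effect is descriptive and concentrated in Part B. Under the assumptions above, a dose group keeps between 86% (*p* = 0.05) and 28% (*p* = 0.5) of the events of one recurring term. It loses little if recurrence is rare or is recorded as one continuing event. Part A is little affected: pooled placebo keeps 92% to 99% over the same range if the A3 periods are merged, and active treatments lose only repeats after a single dose.

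**What to change.** Limit the rule in SAP Section 7.7.1, for example:

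> For the number of subjects, a subject is counted once per preferred term and treatment, at maximum severity. For the number of TEAEs, every distinct TEAE is counted; one episode recorded on several lines because its severity changed counts once.

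Also state whether placebo fasted and placebo fed in Group A3 are one treatment or two for this purpose.

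If the collapsed count is intended, keep the rule and declare it in Section 9 as a change to how the primary endpoint is counted.

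Secondary, and only if the table shells do not already have them: add event counts to the system organ class and preferred term tables, as Protocol Section 8.5 implies, and a by-treatment summary of TEAEs per subject.

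The cost is two or three sentences in Section 7.7.1, or one in Section 9. No new data are needed.

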### 7.7.2. Clinical Laboratory Parameters

All clinical laboratory parameters and their changes from baseline will be listed; any value outside the clinical reference range will be flagged. Separate listings will be provided for any parameter for which there is any individual subject value outside the respective clinical reference range.

Summary tables and boxplots by treatment and timepoint will be provided for clinical chemistry, hematology, and coagulation parameters and their changes from baseline.

Shifts from baseline tables will be provided for clinical chemistry, hematology and coagulation parameters.

Values recorded as  $<x$ ,  $\leq x$ ,  $>x$ , or  $\geq x$  will be displayed in the listings as recorded. For the derivation of listing flags, all calculations, and presentation in the figures,  $<x$  and  $\leq x$  values will be set to half of  $x$ , whereas  $>x$  and  $\geq x$  values will be set to  $x$ .

### **7.7.3. Vital Signs Parameters**

All vital signs parameters and their changes from baseline will be listed; any value outside the clinical reference range will be flagged.

Summary tables and boxplots by treatment and timepoint will be provided for all vital signs parameters and their changes from baseline.

Shifts from baseline tables will be provided for vital signs parameters.

### **7.7.4. 12-lead Electrocardiogram Parameters**

All 12-lead ECG parameters and their changes from baseline will be listed; any value outside the clinical reference range will be flagged.

Summary tables and boxplots by treatment and timepoint will be provided for all 12-lead ECG parameters and their changes from baseline.

Shifts from baseline tables will be provided for 12-lead ECG parameters.

### **7.7.5. Other Assessments**

Medical history will not be listed.

All other safety and tolerability assessments not detailed in the above sections will be listed only.

### **7.7.6. Safety and Tolerability Statistical Methodology**

No inferential statistical analyses are planned.

## **8. INTERIM ANALYSES**

No formal interim analyses are planned for this study.

## **9. SIGNIFICANT CHANGES FROM THE PROTOCOL-SPECIFIED ANALYSES**

The statistical analysis for the food effect group (A3) was changed to use a mixed model which differs from the stated analysis of variance model in the protocol.

## 11. APPENDICES

### Appendix 1: Document History

Status and Version	Date of Change	Summary/Reason for Changes
Final Version 1.0	NA	NA; the first version.

NA = not applicable
